8.7 Study Drug Administration

Study drug administration for Revcovi will be summarized by subject status based on the prescribing data for Adagen/Revcovi Treatment. For subjects transitioning from the STP-2279-002 study, study drug administration will be summarized from the first dose of Revcovi in the CLI-06814AA1-01 study until the end of the CLI-06814AA1-01 registry.

Duration of treatment (months treated) is the number of days on treatment based on the first and last days of treatment with the study drug (last day of study drug – first day of study drug + 1)/30.4375. For subjects who are still taking Revcovi at the end of the observational period,

the duration will be counted until the date of study completion or study discontinuation, respectively, as reported on the study disposition page. Duration of treatment will be summarized by descriptive statistics.

The number of doses administered will be summarized by descriptive statistics. The number of doses will be calculated by the number of weeks x number of times per week for each treatment period and summed for each subject.

Frequency statistics will be calculated for the number of subjects with dose modifications and for subjects with dose omissions/delays will be calculated. A dose omission/delay will be defined as a dose interruption of 8 days or more. The duration of the dose interruption will be calculated as start of the subsequent treatment period – end date of the previous treatment period + 1 day. The duration of dose interruptions will be summarized on subject level, i.e. multiple dose interruptions will be summed on subject level and summarized by descriptive statistics. Duration of dose interruptions will be calculated as an absolute value and as percentages of the duration of treatment.

The total weekly dose of Revcovi (in mg/kg) will be summarized for each suggested visit. This is defined as the dose on the targeted study day. If a new dose is started on the targeted study day, the new dose is used as weekly dose. The weekly dose is calculated as dose per administration (mg) x number of times per week.

Prescribing data of Revcovi will also be presented in a data listing. Revcovi administration data from the subject diary will be listed but not summarized.

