13.3 Baseline and Assignment to Suggested Study Visits

For Adagen-naïve patients and Adagen-transitioning patients, baseline will be defined as the last measurement for a variable with a non-missing value prior or on the treatment start date with Revcovi in this study (CLI-06814AA1-01). For STP 2279-002 subjects, the baseline will be defined as the last measurement for a variable with a non-missing value prior or on the treatment start date with Revcovi in STP 2279-002. At Study Day 1, it is assumed that all assessments are performed prior to the application of the first dose of Revcovi. However, adverse events with the same onset date as the start date of Revcovi will be assumed to be post-treatment and counted as treatment-emergent AEs.

Assessments will be 'slotted' to the treatment visits as described below. Reference date for all visits will be the start date of Revcovi (Study Day 1). Study Day 1 for the subjects transitioning from the STP-2279-002 study will be the reported start date of Revcovi in the STP-2279-002 study. Depending on the subject status (Adagen-Naïve subject or Adagen transitioning subject), the suggested visit schedule is different for the first 9 treatment months. For the Adagen-Naïve subjects, there are more suggested visits compared to the Adagen transitioning subjects. Participants of the STP 2279-002 study will be analyzed according to the Schedule of Assessments for Adagen-Transitioning Subjects. The visit windows will be defined for all assessments as follows:

Suggested Visit	Targeted Study Day	Visit window (Study Day)					
Enrollment/Baseline	Last available data	$-\infty$ to 1					
	prior or at Study Day 1						
TW 4	30	2-45					
TW 8	60	46-75					

Adagen-Transitioning subjects

Chiesi Farmaceutici S.p.A. Statistical Analysis Plan CLI-06814AA1-01 Version 4.0 06June2023

TM 6 TM 9 TM 12	182 273	137-227 228-319
		228-310
TM 12		
	365	320-410
TM 15	456	411-501
TM 18	547	502-592
TM 21	638	593-684
TM 24	730	685-776
TM 27	822	777-867
TM 30	913	868-958
TM 33	1004	959-1049
TM 36	1095	1050-1141
TM 39	1187	1142-1232
TM 42	1278	1233-1324
TM 45	1370	1325-1415
TM 48	1461	1416-1506
TM 51	1552	1507-1597
TM 54	1643	1598-1689
TM 57	1735	1690-1780
TM 60	1826	1781-1871
TM 63	1917	1872-1962
TM 66	2008	1963-2055
TM 69	2100	2056-2145
TM 72	2191	2146-2236
TM 75	2282	2237-2328
TM 78	2374	2329-2419
TM 81	2465	2420-2510
TM 84	2556	2511-2601
TM 87	2647	2602-2693
TM 90	2739	2694-2784
TM 93	2830	2785-2875
TM 96	2921	2876-2966
TM 99	3012	2967-3057

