14. PROGRAMMING SPECIFICATIONS

- The following algorithm should be used to estimate adverse event start dates for which only partial information is known. To conservatively assign start dates as early as possible, the first day on study drug is the reported start date of Revcovi in the CLI-06814AA1-01 study.
 - Missing day and month
 - If the year is the same as the year of first day on drug, then the day and month of the start date of drug will be assigned to the missing fields.
 - If the year is prior to the year of first day on drug, then December 31 will be assigned to the missing fields.
 - If the year is after the year of first day on drug, then January 01 will be assigned to the missing fields.
 - Missing month only
 - Treat day as missing and replace both month and day according to the above procedure.
 - o Missing day only
 - If the month and year are the same as the year and month of first day on drug, then the start date of drug will be assigned to the missing day.
 - If the month and year are before the year and month of first day on drug, then the last day of the month will be assigned to the missing day.
 - If the month and year are after the year and month of first day on drug, then the first day of the month will be assigned to the missing day.

If the resultant imputed start date is after the AE stop date (and the AE stop date is complete), the imputed start date will be reset to the AE stop date.

- Adverse events with partially missing stop dates and the outcome is "Resolved" or "Resolved with sequelae" will have stop dates imputed as follows:
 - *year is missing* date left missing.
 - o month is missing impute 'December'.
 - o *day is missing* impute 'last date of that month'.

- It is assumed that for the start and stop date of Revcovi, at least month and year are known. If day is missing, it will be imputed by the first of the month, if necessary.
- Partially missing start dates for Adagen pre-treatment (Adagen transitioning patients) will be imputed as follows:
 - Day is missing impute 01 of the month
 - Day and month is missing: impute 01July.
- It is assumed that at least month and year is known for the QoL questionnaires, physical examinations, vital signs, and other laboratory data. If the day is missing, day will be imputed by the 15th of the month. If month and/or year is missing, the records will be excluded from all analyses.
- Partially missing dates for the diagnosis of ADA-SCID will be imputed as follows:

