 - Year is missing impute with date of birth
 - Month is missing and year is available impute by 01 January. If the imputed date is prior to the date of birth, impute date of birth.
 - Day is missing impute first day of month. If this imputed date is prior to the date of birth, impute date of birth.
- Complete dates for concomitant medications with missing or partially missing start dates will be imputed, if necessary, using the same algorithm described for adverse event onset dates. If the stop date is missing or partially missing and the "ongoing" variable is indicated as 'no', the imputation rule is applied in the following order:
 - *year is missing* the medication will be considered to have been received at all periods after that period determined by the start date. Date is left missing.
 - o month is missing impute 'December'.
 - o *day is missing* impute 'last date of that month'.
- The following algorithm should be used, when necessary, to calculate a start date that is partially missing for medical history:
 - missing day and month January 01 will be assigned to the missing fields.
 - *missing month only* treat day as missing and replace both month and day according to the above procedure.
 - *missing day only* assign first of the month to the missing day.
- Partially missing stop dates will be imputed as:
 - *year is missing*, no imputation. Date left missing.

- *month is missing and year is prior to year of first dose of study medication*impute 'December'.
- month is missing and year the same as the year of the first dose of study medication impute same month as in start date.
- \circ day is missing: impute 'last date of that month'. If this results in a date \geq the date of the first dose of study medication, impute day as the day prior to the first dose of study medication.
- Partial missing death dates will be imputed in the same way as adverse event start dates.
- Date imputations will be applied to the process of assigning study day and should be retained in the analysis datasets, but the data listings should display the original, partially missing dates.
- Adverse event summary tables will only include treatment-emergent AEs. However, listings will include all AEs (i.e., treatment-emergent and non treatment-emergent AEs) with the non treatment-emergent AEs flagged.

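### A missing day in a Revcovi stop date is set to the first of the month with no bound, which cuts exposure, closes the 30-day windows early and can create false dose interruptions

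*SAP*

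**What the plan says.** SAP Section 14 (Programming Specifications) covers partial treatment dates in one bullet: "It is assumed that for the start and stop date of Revcovi, at least month and year are known". The next sentence applies to both dates: "If day is missing, it will be imputed by the first of the month, if necessary". No floor or ceiling is attached.

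The same section states that "Date imputations will be applied to the process of assigning study day and should be retained in the analysis datasets". The other relevant rules are:

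- **Exposure (SAP 8.7):** duration is the "number of days on treatment based on the first and last days of treatment with the study drug". Subjects still on drug are counted to study completion or discontinuation.
- **Interruptions (SAP 8.7):** "A dose omission/delay will be defined as a dose interruption of 8 days or more".
- **Event windows (SAP 7.2.3, 8.2 and 13.5):** treatment-emergent adverse events end 30 days after the last dose. Last treatment plus 30 days is one of the dates that can end an infection or hospitalization period.
- **Baseline (SAP 13.3):** "baseline will be defined as the last measurement for a variable with a non-missing value prior or on the treatment start date".
- **Laboratory, vital-sign and quality-of-life dates (SAP 14):** "If the day is missing, day will be imputed by the 15th of the month".

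Elsewhere in Section 14, stop dates of adverse events and concomitant medications that lack a day go to the end of the month. An imputed adverse event start is pulled back to a complete stop date if it would fall later, and a diagnosis date cannot precede birth. The Revcovi rule has no such check.

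**The concern.** A first-of-month start and a first-of-month stop do different things. The early start is a defensible choice, since it counts more adverse events as treatment-emergent. The early stop removes time in which the subject may have been on drug, and it also removes follow-up after the last dose.

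The stop date feeds several outputs: treatment duration, number of doses, dose omissions or delays, treatment-emergent status, and infection and hospitalization counts with their person-time. One wrong date therefore affects all of them. The effect is proportionally largest in subjects on short courses; SAP 2.1 describes patients expected to have 3 to 4 months of enzyme replacement before transplantation or gene therapy.

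**Working it through.** The plan gives no figure to reproduce, so I applied its own rules to dates.

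**Formulas (SAP 8.7)**
- Exposure in days = last day − first day + 1 (then divided by 30.4375 for months).
- Gap = next start − previous stop + 1, counted as an omission or delay at 8 or more.

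**Assumption for averages.** The true missing day is equally likely to be any day of its month. I enumerated all 1,461 days of a four-year cycle. The documents do not say how often a day is missing.

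**1. Size of the shift.** Moving a date to the first of its month moves it earlier by a mean of 14.7 days, at most 30.

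**2. Exposure, stop day missing and start known**
- On a 3- to 4-month course (91 to 122 days) the mean cut is 14.7/122 = 12% to 14.7/91 = 16%. The maximum is 30/122 = 25% to 30/91 = 33%.
- True course 20 March to 28 June: 101 days. With the stop day missing: 74. With the start day missing: 120. With both missing: 93.
- Start known as 10 March, true stop 31 March, stop day missing: 1 March − 10 March + 1 = −8 days, against a true 22.

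**3. Event windows**
- True last dose 28 March: the 30-day window should end 27 April but ends 31 March, 27 days early.
- True last dose 31 May: it should end 30 June but ends 31 May, 30 days early, so none of the follow-up after the last dose remains.
- Adverse events in the lost days leave the summary tables. Infections leave the rates unless another end date, such as transplantation, has already closed the period.

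**4. Interruptions, stop day missing and next start known**
- Stop in March, next period starting 1 April: 1 April − 1 March + 1 = 32 days. Had dosing run to 31 March, the formula would give 2.
- In general, if the true stop is day k of the month and the next period starts the day after, the computed gap is k + 1, so it is flagged whenever k is 7 or more. The unflagged days are 6 × 48 months = 288 of 1,461, so 1,173/1,461 = 80% of truly back-to-back periods are falsely flagged. The mean computed gap is 14.7 + 2 = 16.7 days.
- If the next start also lacks its day, both dates go to the first. A false flag then needs the stop on the last day of a month: 48/1,461 = 3.3%.

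**5. Start day missing**
- True start 20 March, pre-dose sample 18 March: truly Study Day −2, but computed as Study Day 18. It is slotted to TW 4 for transitioning subjects (window 2–45) or TW 2 for naïve subjects (window 1–22).
- If the sample in that month also lacks its day, it is set to the 15th and becomes Study Day 15.

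**6. Month-end stop for comparison.** Before any cap it lengthens exposure by a mean of 14.7 days, at most 30. It produces no false gap between back-to-back periods, but without a cap at the next period the gap is zero or negative in 93% of cases.

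**The case against.** The strongest reply is that month-end imputation exchanges one bias for another. If the true last dose was 5 March and the next period began on 1 April, the real gap is 28 days by the SAP formula; a month-end stop gives 2 and hides it. Added person-time can also dilute infection and hospitalization rates. This stands, and it is why the month-end rule needs caps and a flag.

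It is also fair that the rule is a contingency. Diaries record dosing dates, and the data capture system runs date checks and manual queries (Protocol 10.10.4 and 14.7.1). Subjects still on drug have no stop date to impute, and excluded events are still listed and flagged. These facts limit how often the problem arises, but they do not make the rule right when it is used.

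Three stronger readings are tempting and not supported:

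- **That partial dates are common.** The documents provide for retrospective collection in subjects who began Revcovi before enrolment (Protocol 7.1), but give no count of such subjects or of missing days.
- **That exposure is always understated.** A first-of-month start lengthens it. With both days missing the errors partly offset, and the net sign depends on the true days.
- **That baseline is always lost, so imputed starts should be moved to follow enrolment samples.** An earlier value serves as baseline if one exists. Enrolment is the date of consent (Protocol 10.2), so in subjects already on Revcovi an enrolment sample can be on-treatment. Tying the start to it could turn treated values into baseline.

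The contrast with adverse event stop dates is not a contradiction in itself, since those dates serve another purpose. It does show that month-end imputation and plausibility checks are already in use in this SAP.

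**Conclusion.** The point holds for the stop date. The rule as written gives an early or even impossible stop, with up to 30 days lost from exposure and up to 30 days from the event windows. It creates a false interruption in about 80% of back-to-back periods where only the stop day is missing, assuming the true day is uniform within the month. The maxima and worked dates need no such assumption.

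For the start date the rule can stay, with one safeguard for samples known to be pre-dose. The effect on the final tables cannot be sized, because the frequency of missing days is not given. No test or error rate is involved. This is a modest correction, best made before database lock.

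**What to change.** In SAP Section 14, replace the single Revcovi bullet with separate rules:

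- **Stop date.** Impute a missing day as the last day of the month, capped at the earliest of the day before the next treatment period, death, transplantation, and study completion or discontinuation. It should never be before the period's own start.
- **Interruptions.** Flag any whose length rests on an imputed date. Count it as a dose omission or delay only if it is 8 days or more under every possible day.
- **Start date.** Keep the first of the month. If a sample is documented as taken before the first Revcovi dose, and is not merely labelled enrolment, keep it as pre-dose or baseline even when imputed dates would place it after Study Day 1.
- **Reporting.** Flag imputed stop dates in the exposure listing and state how many there are, since some exposure and person-time may be overstated and some real gaps missed.

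The cost is a few sentences and a short programming change. No new data are needed beyond any existing record that a sample was pre-dose.

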5.1 Disease Background

Adenosine deaminase (ADA)-deficient combined immunodeficiency disease is a rare, inherited, and often fatal disease. It is characterized by severe and recurrent opportunistic infections, failure to thrive, profound lymphopenia with absent or severely impaired cellular and humoral immune function, and metabolic abnormalities (Booth and Gaspar 2009, Gaspar et al., 2009). These patients are lymphopenic at birth and predisposed to recurrent illnesses caused by pathogens and opportunistic organisms that often begin within a few weeks. The average age at diagnosis for patients with ADA-SCID is within first few months of life (Arredondo-Vega et al., 1998). The incidence of ADA deficiency is estimated to be between 1:200,000 and 1:1,000,000 live births (Gaspar et al., 2009).

ADA deficiency can be categorized into four phenotypes (Booth and Gaspar 2009):

- **Early onset**: The largest number of patients with ADA deficiency (about 85% to 90%) present with early onset ADA-SCID, which is the most severe form of the immunodeficiency. Patients are usually diagnosed within first few months of life and almost always by the age of 1 year.
- **Delayed onset ADA deficiency** has been identified in 10% to 15% of patients with ADA deficiency. The disease presents itself after the first year of life and is most likely related to the specific ADA mutation that in such cases results in some residual ADA activity and less profound lymphopenia and immune function.
- Late (or adult) onset ADA deficiency has been identified in some individuals but is less common than early or delayed-onset forms.
- **Partial ADA deficiency** can be an incidental finding in a healthy individual who has normal immune function and abnormal ADA expression in erythrocytes. Partial ADA deficiency is extremely rare.

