6.5 Medical History

Medical history at screening will be listed, but not summarized.

6.6 **Prior ADA-SCID Treatment excluding ERT**

The number and percentages of patients who received prior ADA-SCID treatment (excluding ERT) will be summarized by type of treatment and overall. Free text for other treatments will be listed but not summarized.

6.7 **Prior ERT Treatments**

Prior ERT medications (Adagen treatment) will be summarized for all subjects transitioning from Adagen to Revcovi and for the STP 2279-002 subjects. The following parameters will be summarized: duration of Adagen treatment (i.e. last dose – first dose +1 day), units per administration, administration frequency, total weekly dose (as reported on the eCRF) and calculated total weekly dose per kg body weight for the prescribed and actual dose. For subjects who were treated according to the prescription, actual dose will be derived from the prescribed dose. The number and percentages of subjects who stopped Adagen treatment prior to the first dose will also be reported together with summary statistics for the time from the last dose of Adagen until the first dose of Revcovi. For the STP 2279-002 subjects, the duration of treatment with Revcovi in the STP 2279-002 study (last dose – first dose of Revcovi in the STP 2279-002 study + 1 day) will be summarized. All prior treatments with Adagen will also be presented in a data listing.

6.8 **Physical Examination**

Physical examination results at screening will be reported as medical history and will be analyzed and presented as such.

6.9 **Protocol Deviations**

A full list of protocol deviations will be presented in the clinical study report. Because this is a registry with no scheduled assessments or planned treatments, on-study protocol violations are restricted to administrative and operational deviations (e.g. delayed reporting of an SAE or transmission of clear names together with SAE reports). Protocol deviations will be listed but not summarized.

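### Partial Adagen start dates are imputed without a bound at birth or at the last Adagen dose, so the prior-Adagen duration can begin before birth or come out zero or negative

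*SAP*

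**What the plan says.** SAP section 14 (Programming Specifications) introduces the rule with "Partially missing start dates for Adagen pre-treatment (Adagen transitioning patients) will be imputed as follows". It has two branches: "Day is missing impute 01 of the month", and "Day and month is missing: impute 01July". Neither carries a condition.

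SAP 6.7 (Prior ERT Treatments) uses the date. Among the quantities summarized for transitioning and STP-2279-002 subjects is "duration of Adagen treatment (i.e. last dose – first dose +1 day", that is, inclusive days from first to last Adagen dose. SAP section 5 lists the minimum and maximum among the statistics reported for every continuous variable.

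Section 14 does bound two comparable imputations. For the ADA-SCID diagnosis date it adds "If the imputed date is prior to the date of birth, impute date of birth". For an adverse event whose imputed start falls after a complete stop date, it adds "the imputed start date will be reset to the AE stop date". Its closing statements on date imputation add no bound for Adagen. They keep imputed dates in the analysis datasets and show the original partial dates in listings.

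**The concern.** A start date imputed from the year alone can contradict dates that are known. Two contradictions are possible: a start before the subject was born, and a start after the subject's last Adagen dose. The first overstates the duration, and the second makes it zero or negative. Because the SAP resets comparable dates in the same section, the missing bound looks like an oversight rather than a choice.

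The before-birth case is realistic in this disease. Protocol 5.1 puts early-onset disease at about 85% to 90% of patients and says of them: "Patients are usually diagnosed within first few months of life and almost always by the age of 1 year". An Adagen start in the birth year is therefore plausible. It can also concern subjects who are now older, since what matters is age when Adagen began.

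At stake is the description of how pretreated the transitioning group is. One affected record could set the reported minimum to an impossible value.

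**Working it through.** The plan states no figure to reproduce, so the check is date arithmetic on the SAP's own rules.

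**Inputs**
- Imputed start: 1 July of the reported year, or day 01 of the reported month (SAP 14).
- Duration = last Adagen dose - first Adagen dose + 1 day (SAP 6.7).
- Birth, start and last-dose dates below are illustrative assumptions; the documents give none.

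**Control case: long treatment.** Start 2015, last dose 31 December 2018. Imputed start 1 July 2015. Duration = 184 + 366 + 365 + 365 = 1,280 days. The possible range runs from 1,097 (start 31 December 2015) to 1,461 (start 1 January 2015). The rule gives a sensible central value.

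**Start before birth.** Born 15 September 2018, start 2018, last dose 31 March 2019.
- Imputed start 1 July 2018, which is 76 days before birth.
- Duration = 184 days (July to December) + 90 days (January to March) = 274.
- Longest possible, from the day of birth: 108 + 90 = 198. Shortest possible, from 31 December 2018: 1 + 90 = 91.
- The result exceeds the maximum by 274 - 198 = 76 days.
- Reset to the date of birth: 198 days.

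The same happens, by 1 to 183 days, for any birth from 2 July to 31 December when the year-only start is in the birth year.

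**Start after the last dose.** Start 2019, imputed 1 July 2019.

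| Last Adagen dose | Duration under the rule | After reset to last dose |
|---|---|---|
| 31 January 2019 | -150 | 1 |
| 31 March 2019 | -91 | 1 |
| 29 June 2019 | -1 | 1 |
| 30 June 2019 | 0 | 1 |
| 1 July 2019 | 1 | 1 |

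Because of the added day, a last dose on or before 29 June gives a negative value, and 30 June gives exactly 0. For a last dose on 31 March 2019 the true duration lies between 1 and 90 days (31 + 28 + 31).

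**Day missing only.** Born 15 September 2018, start September 2018: imputed 1 September, 14 days before birth. A start after the last dose cannot arise here if the reported months are consistent, since day 01 is never later than a dose in the same or a later month.

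**The case against.** The strongest reply concerns reach. The documents do not say how many Adagen start dates are known only to the year, so the number of affected subjects may be zero. Transitioning subjects are described as being on chronic Adagen. A zero or negative duration needs the whole course inside one calendar year, ending by 30 June, with the start month unknown. A start that recent is one whose month is likely to be on record; year-only dates are likelier for starts long ago, where the control case shows the rule behaving well. That is inference, but it is reasonable, and it makes the negative case the less likely of the two.

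The consequence is also contained. The SAP defines no efficacy, safety, exposure or survival analysis from the Adagen start; study day and visit windows run from the first Revcovi dose (SAP 13.2 and 13.3). All analysis is descriptive. A negative minimum would be conspicuous, and the listings show which start dates were partial.

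All of this stands as a limit on size. It does not remove the defect: followed exactly, the rule yields impossible values, and a before-birth start is not conspicuous, because 274 days looks like an ordinary duration.

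A reader might infer that about half of year-only records go wrong, since 183 of 365 birth dates (50%) fall after 1 July and 180 of 365 last-dose dates (49%) fall on or before 29 June. The documents do not support that. Those shares assume evenly spread dates, and each applies only to year-only records that also start in the birth year, or that also start and stop in the same year. They are not shares of the transitioning group.

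**Conclusion.** The point holds, and it is minor. The unconditional imputation in SAP 14, fed into the SAP 6.7 formula, can place an Adagen start before birth, or give a duration of zero or less. Nothing in either document prevents this.

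For a single affected record the error can exceed the longest possible duration by up to 183 days. Across the study the size is unknown, because the count of partial dates is not given. The damage is confined to the descriptive prior-ERT summary, chiefly its minimum, and it matters most for infants and short exposures. The documents do not support reading it as a threat to any efficacy or safety result.

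There is one related gap. The rule's heading names transitioning patients only, while SAP 6.7 also summarizes Adagen duration for STP-2279-002 subjects, so the treatment of their partial dates is left unstated.

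**What to change.** Add two resets to SAP 14, applying to both the day-missing rule and the day-and-month-missing rule. First, use the wording the SAP already has for the diagnosis date: "If the imputed date is prior to the date of birth, impute date of birth". Second, if the imputed start is later than the last Adagen dose, set it to the date of that dose, as is done for adverse event starts. State that the rule also covers STP-2279-002 subjects.

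The cost is a sentence or two and a few lines of code. Resetting to a bound has a known price: a start moved to birth gives the longest possible duration, and a start moved to the last dose gives 1 day, the shortest. The 1-day values should be footnoted as imputed.

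Two refinements are better left out. Using a midpoint only when a bound binds creates a jump: a child born 30 June keeps 1 July, while one born 2 July moves to about 1 October. Adding the diagnosis date as a further lower bound assumes that Adagen never precedes the recorded diagnosis, which the documents do not establish.
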